7.6 Return to Mayo Clinic

For this protocol, the patient must return to the Mayo Clinic for evaluation for Cycles 1-3 and then at least every 3 cycles. After the first 3 cycles, clinical evaluation and blood tests

can be obtained per test schedule and mailed/faxed to Mayo Clinic and patient can return at least every 3 cycles for follow up to Mayo Clinic. Adverse events will be collected at the end of each cycle by telephone call.

Only enough lenalidomide for one cycle of therapy will be supplied to the patient each cycle. All study participants must be registered into the mandatory REVLIMID REMS™ program, and be willing and able to comply with the requirements of REVLIMID REMS™.

After the first 3 cycles, lenalidomide and anakinra may be mailed out monthly to the patient if clinical evaluation and blood tests can be obtained per test schedule. Patient can return at least every 3 cycles for follow up to Mayo. Prescription for dexamethasone will be provided.

7.7 Breaking Codes in Double-Blinded Studies

Situations requiring codes to be broken: There are three distinct situations in which it is appropriate to break the codes for individual patients enrolled in double-blind trials:

- (1) In the event of an emergency for an individual patient.
- (2) In the event that it would be helpful for the future clinical care of an individual patient after she/he has completed participation in the trial.
- (3) When it is necessary to know the specific treatment assignment of each patient in the trial in order to manage them all appropriately after they have completed participation in the trial. Example: There is a blinded arm that contains a steroid, narcotic, or other medication that must be carefully reduced in order to prevent physiological damage. [This one is rare--there are no currently active protocols of this type.]

In the event of an emergency, call the MCCC Registration Office at [REDACTED] to break the code on Monday through Friday, 8:00 a.m. to 4:30 p.m. Central Time. If the code must be broken after hours, assume the patient was assigned to active treatment and treat accordingly. Place a call to the MCCC Registration Office and leave a message informing them of the need to un-blind a patient. Provide your contact information so that MCCC Registration Office personnel can return the call the next business day.

If, in the judgment of the attending physician, it would be helpful for the future clinical care of the individual patient, the code may be broken *after* the patient has completed the study. That is, after the patient has been fully evaluated and all evaluation information has been recorded by the attending physician and the patient (if appropriate), the MCCC Registration Office may be called [REDACTED] to find out which study therapy the patient was receiving.

8.0 Dosage Modification Based on Adverse Events

Strictly follow the modifications in this table for the first **two** cycles, until individual treatment tolerance can be ascertained. Thereafter, these modifications should be regarded as guidelines to produce mild-to-moderate, but not debilitating, side effects. If multiple adverse events are seen, administer dose based on greatest reduction required for any single adverse event observed. Reductions or increases apply to treatment given in the preceding cycle and are based on adverse events observed since the prior dose.

ALERT: *ADR reporting may be required for some adverse events (See Section 10)*

8.1 Dose Levels (Based on Adverse Events in Tables 8.2)

Dose Level	Lenalidomide
Starting Dose	25 mg days 1-21 every 28 days
-1	15 mg days 1-21 every 28 days
-2	10 mg days 1-21 every 28 days
-3	5 mg days 1-21 every 28 days

Dose Level	Anakinra
Starting Dose	100 mg SQ daily
-1	100 mg SQ every other day
-2*	100 mg SQ every 3rd day

*If patients unable to tolerate -2 they will go off treatment to event monitoring

8.11 Instruction for initiation of a new cycle of therapy

A new course of treatment may begin on the scheduled day 1 of a new cycle if:

- The ANC is $\geq 1,500/\mu\text{L}$;
- The platelet count is $\geq 75,000/\mu\text{L}$;
- Any drug-related injection site reaction or peripheral sensory neuropathy that may have occurred has resolved to \leq Grade 1 severity;
- Any other drug-related adverse events that may have occurred have resolved to \leq Grade 2 severity;
- If these conditions are not met on Day 1 of a new cycle, the subject will be evaluated weekly and a new cycle of treatment will not be initiated until the toxicity has resolved as described above. If lenalidomide dosing was halted during the previous cycle and was restarted with a one-level dose reduction without requiring an interruption for the remainder of the cycle, then that reduced dose level will be initiated on Day 1 of the new cycle. **If lenalidomide dosing was omitted for the remainder of the previous cycle or if the new cycle is delayed due to toxicity newly encountered on the scheduled Day 1, then the new cycle will be started with a one-level dose reduction of lenalidomide.**

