8.2 Dose Modifications of Lenalidomide during a Cycle of Therapy

Dose reductions of one drug and not the other may be done at the investigators discretion based on attribution of adverse events except neutropenia in which lenalidomide should be decreased first before anakinra.

→ → Use the NCI Common Terminology Criteria for Adverse Events (CTCAE) version 4.0* unless otherwise specified ← ←

CTCAE System/Organ/Class (SOC)	ADVERSE EVENT	AGENT	ACTION** Days 2-14 of cycle	ACTION** Day ≥15 of cycle
Blood and lymphatic system disorders	Febrile neutropenia associated with fever (temperature ≥38.5°C)	Lenalidomide	Omit lenalidomide dose. Follow CBC weekly. If neutropenia has resolved to ≤Grade 2 prior to Day 21, restart lenalidomide at next lower dose level and continue the cycle through Day 21. If neutropenia is the only toxicity for which a dose reduction is required, G-CSF may be used and the lenalidomide dose maintained	Omit lenalidomide for remainder of cycle. See Section 8.11 for Initiation of a New Cycle and reduce the dose of lenalidomide by 1 dose level. If neutropenia is the only toxicity for which a dose reduction is required, G-CSF may be used and the lenalidomide dose maintained for the next cycle at the investigator's discretion.
Investigations	Platelet count decreased ≥ Grade 3 (platelet count <50,000/mm ³)	Lenalidomide	Omit lenalidomide dose Follow CBC weekly Hold anticoagulation until platelets >50,000 If thrombocyte-penia resolves to ≤Grade 2 prior to Day 21, restart lenalidomide at next lower dose level and continue the cycle through Day 21	Omit lenalidomide for remainder of cycle See Section 8.11 , Instructions for Initiation of a New Cycle and reduce the dose of lenalidomide by 1 dose level

CTCAE System/Organ/Class (SOC)	ADVERSE EVENT	AGENT	ACTION** Days 2-14 of cycle	ACTION** Day \geq 15 of cycle
Skin and subcutaneous tissue disorders	Rash maculo papular Grade 2 or 3.	Lenalidomide	Omit lenalidomide dose Follow weekly If the event resolves to \leq Grade 1 prior to Day 21, restart lenalidomide at next lower dose level and continue the cycle through Day 21	Omit lenalidomide for remainder of cycle See Section 8.11 , Instructions for Initiation of a New Cycle and reduce the dose of lenalidomide by 1 dose level
	Any rash Grade 4	Lenalidomide	Discontinue lenalidomide	Discontinue lenalidomide

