Nervous System Disorders	Peripheral sensory neuropathy Grade 3	Lenalidomide	Omit lenalidomide dose Follow at least weekly If the event resolves to \leq Grade 1 prior to Day 21, restart lenalidomide at next lower dose level and continue the cycle through Day 21	Omit lenalidomide for the remainder of the cycle. See Section 8.11 Instructions for Initiation of a New Cycle and reduce the dose of lenalidomide by 1 dose level
	Peripheral sensory neuropathy Grade 4	Lenalidomide	Discontinue lenalidomide	Discontinue lenalidomide
Immune system disorders	Allergic reaction Grade 2-3	Lenalidomide	Omit dose Follow at least weekly If the toxicity resolves to \leq Grade 1 prior to Day 15 restart at next lower dose level and continue the cycle until Day 21	Omit lenalidomide for the remainder of the cycle If the adverse event resolves to \leq Grade 1, reduce dose 1 level in next cycle If adverse event recurs, discontinue therapy
	Grade 4	Lenalidomide	Discontinue lenalidomide	Discontinue lenalidomide
Vascular disorders	Thromboembolic event \geq Grade 3	Lenalidomide	Omit dose and start anticoagulation; restart at investigator's discretion (maintain dose level)	Omit lenalidomide for remainder of cycle and start anticoagulation. Maintain dose level in next cycle

CTCAE System/Organ/Class (SOC)	ADVERSE EVENT	AGENT	ACTION** Days 2-14 of cycle	ACTION** Day \geq 15 of cycle
Endocrine disorders	Hyperthyroidism or Hypothyroidism \geq Grade 2	Lenalidomide	-Omit lenalidomide for remainder of cycle, evaluate etiology, and initiate appropriate therapy. -See Instructions for Initiation of a New Cycle and reduce the dose of lenalidomide by 1 dose level	Omit lenalidomide for remainder of cycle, evaluate etiology, and initiate appropriate therapy. See Section 8.11 , Instructions for Initiation of a New Cycle and reduce the dose of lenalidomide by 1 dose level
Other non-hematologic adverse event	Other non-hematologic toxicity \geq Grade 3	Lenalidomide	-Omit lenalidomide dose. Follow at least weekly. If the toxicity resolves to \leq Grade 2 prior to Day 21, restart lenalidomide at next lower dose level and continue the cycle through Day 21	Omit lenalidomide for remainder of cycle. See Section 8.11 , Instructions for Initiation of a New Cycle and reduce the dose of lenalidomide by 1 dose level.

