8.3 Dose Modifications of Anakinra/Placebo during a Cycle of Therapy

Dose reductions of one drug and not the other may be done at the investigators discretion based on attribution of adverse events except neutropenia in which lenalidomide should be decreased first before anakinra.

CTCAE System/organ/Class (SOC)	ADVERSE EVENT	AGENT	ACTION ** (each cycle)
Blood and lymphatic system disorders	Febrile Neutropenia \geq Grade 3	Anakinra/ Placebo	For ANC <1000, omit anakinra/placebo until ANC \geq 1500. Then restart anakinra or placebo with the dose reduced one dose level.
Infections and Infestations	Infection/Febrile Neutropenia \geq Grade 2		Omit until infection resolved; then restart at same dose
	Infection/Febrile Neutropenia \geq Grade 3		Omit until infection resolved; then restart anakinra or placebo with the dose reduced one dose level
Other non-hematologic adverse event	Any adverse event \geq Grade 3		Omit until toxicity reduces to \leq grade 2; then restart anakinra or placebo with the dose reduced one dose level

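### Section 8.11 accepts a Grade 2 allergic reaction when lenalidomide restarts in a new cycle; the 8.2 allergic-reaction row asks for Grade 1 or less, and neither rule is given precedence

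*Combined protocol and SAP*

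**What the plan says.** Section 8.11 lists what must be true before a new cycle may begin on its scheduled Day 1. Besides the neutrophil and platelet limits, it holds two drug-related event types, injection site reaction and peripheral sensory neuropathy, to Grade 1 or less. The residual condition reads "Any other drug-related adverse events that may have occurred have resolved to" Grade 2 or less. If the conditions are not met, the patient is evaluated weekly and the cycle waits. The section then fixes the dose: if lenalidomide was omitted for the remainder of the previous cycle, or the new cycle is delayed by a new toxicity, "then the new cycle will be started with a one-level dose reduction of lenalidomide".

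The allergic-reaction row of the table in 8.2 covers Grade 2 to 3. From Day 15 it omits lenalidomide for the rest of the cycle. If the reaction resolves to Grade 1 or less, the instruction is to "reduce dose 1 level in next cycle If adverse event recurs, discontinue therapy". The cell does not refer to 8.11 and does not say what to do if the reaction stays at Grade 2. Grade 4 has its own line, which discontinues lenalidomide.

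Section 8.0 makes the table strict for the first two cycles and continues: "Thereafter, these modifications should be regarded as guidelines to produce mild-to-moderate, but not debilitating, side effects".

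**The concern.** The same patient on the same day can meet the entry rule in one section and fail the resumption rule in another. With a Grade 2 allergic reaction on Day 1, an investigator who follows 8.11 restarts lenalidomide one level lower; one who follows the 8.2 row withholds it. Both would be following written instructions.

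What is at stake is patient safety and uniform conduct. The 8.2 row treats these reactions seriously, since a recurrence ends therapy, yet 8.11 as written re-exposes a patient whose reaction to the suspected drug has not settled.

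**Working it through.** No arithmetic is involved, and the plan states no figure to reproduce. The check sets the two rules side by side and then looks for text that ranks them.

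**Step 1. Compare by grade on Day 1**, for a patient whose lenalidomide was omitted for the rest of the previous cycle because of an allergic reaction:

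| Grade on Day 1 | Section 8.11 | 8.2 allergic-reaction row | Same result? |
|---|---|---|---|
| 0 or 1 | Cycle may start; lenalidomide one level lower | Condition met; lenalidomide one level lower | Yes |
| 2 | Cycle may start; lenalidomide one level lower | Condition not met | No |
| 3 | Cycle waits, weekly evaluation | Condition not met | Yes |
| 4 | Cycle waits, weekly evaluation | Lenalidomide discontinued | Yes: not given that day |

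The rules part at Grade 2 only.

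**Step 2. Check the earlier column of the same row.** For Days 2 to 14 the row allows an in-cycle restart if the reaction is down to Grade 1 or less before Day 15. It gives no next-cycle rule for a reaction that has not resolved by then. Such a patient has also had lenalidomide omitted for the rest of the cycle and can reach the same disagreement on the next Day 1.

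**Step 3. Look for a ranking rule.**

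- Section 8.0 makes the table strict and then advisory, but does not rank it against 8.11. Its instruction to use the greatest reduction concerns several adverse events in one patient, not two rules for one event.
- The opening note of 8.2 gives discretion over which drug to reduce, not over which grade applies.
- The notes after 8.4 deal with re-escalation, further reductions and staying on study when an agent is stopped.
- Section 7.4 reuses 8.11 as the restart condition after stem cell collection and says nothing about 8.2.

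None of these settles the matter.

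**Step 4. Check whether the other rows share the problem.**

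- Maculopapular rash ("Rash maculo papular Grade 2 or 3"): the Day 15 onward cell sends the reader to 8.11, so Grade 2 at cycle start is the stated rule.
- Thyroid events ("Omit lenalidomide for remainder of cycle, evaluate etiology, and initiate appropriate therapy"): this row also refers to the new-cycle instructions.
- Infection of Grade 2 or more, for anakinra/placebo in 8.3 ("Omit until infection resolved; then restart at same dose"), and confusion or mood alteration, for dexamethasone in 8.4: each sets its own resumption condition. The dose sentence in 8.11 names lenalidomide only, so a cycle can start with the other agent still omitted. These rows need not conflict with 8.11.

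Allergic reaction is the one row that sets its own next-cycle grade for lenalidomide, stricter than 8.11, without referring to it.

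**Step 5. Check the statistical design.** Section 16.31 rests on medians of 20 and 40 months, a one-sided 0.05 level, 80% power, 45 evaluable patients per arm and 52 progressions. None of these takes the restart grade as an input.

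**The case against.** The best reply is that the two texts can be read together. The 8.2 condition works by implication: it gives an action for a resolved reaction and is silent on an unresolved one, so it does not expressly forbid lenalidomide at Grade 2. Section 8.11 is permissive about starting a cycle, and its dose sentence can be read as fixing the level rather than ordering the drug. The event-specific row is the natural one to follow. Other rows also depart from the general rule: the thromboembolic row says "Maintain dose level in next cycle", and the febrile neutropenia row allows G-CSF with the dose maintained. A careful investigator would probably withhold lenalidomide.

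Much of this stands, and it is why the point is minor. It does not remove the point. That the specific row prevails is a fair inference, but it is not written down, and the wording "then the new cycle will be started with a one-level dose reduction of lenalidomide" cuts against treating 8.11 as a mere choice of level.

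A reader might go further and call the rash row an error, because lenalidomide can start on Day 1 at a grade that triggers omission from Day 2. The documents do not support that: the row defers to 8.11, so the texts do not contradict each other. A Grade 1 requirement for rash would be a clinical choice.

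**Conclusion.** The inconsistency is real, minor and limited to allergic reaction at Grade 2 on Day 1 of a new cycle. It rests on reading the conditional in the 8.2 row as a requirement for resuming lenalidomide, which is the natural reading but not an express prohibition. It matters most while the table is strict, in the first two cycles; later the table is guidance. Phase I patients have gone off study treatment (section 13.0), so any practical effect is on phase II.

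Two stronger conclusions might be inferred, and neither is supported.

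- *How often it happens.* Section 15.17 lists hypersensitivity under 1% for lenalidomide, but in a list limited to important or life-threatening events. It also says that the frequency of further reported reactions, allergic conditions among them, cannot be reliably estimated. No count of affected patients can be drawn from this.
- *Bias between arms.* Both phase II arms receive lenalidomide on the same schedule (7.12). Anakinra has its own listed hypersensitivity reactions (15.37), so equal numbers of allergic reactions cannot be assumed, but nothing in the documents shows a bias in time to progression or its direction.

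No endpoint, power or sample-size figure changes.

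**What to change.** Add to 8.11: *Lenalidomide is not given in a new cycle until any lenalidomide-related allergic reaction has resolved to Grade 1 or less; where a row in 8.2 to 8.4 sets a stricter condition for resuming an agent, that row prevails for that agent.*

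The first clause settles allergic reaction, including one that began on Days 2 to 14 and did not resolve. The second writes down the precedence that a careful reader would assume. It leaves the thromboembolic and G-CSF provisions alone, since they are not stricter, and leaves rash and thyroid events under 8.11, to which their rows refer. The first clause holds lenalidomide only, so it does not itself delay anakinra/placebo or dexamethasone.

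No tests or patients are added: weekly follow-up already appears in 8.11 for a delayed cycle and in the Days 2 to 14 cell of the allergic-reaction row. The downside is that a few patients start lenalidomide later in a cycle, and the definition of an omitted dose after 8.4 says that it is not made up. If the course still ends on Day 21, each week of waiting costs 7 of 21 dosing days in that cycle (7/21 = 33%).

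Whether to ask for Grade 1 for maculopapular rash as well is for the clinical team and is not needed to correct the text.

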Drugs that affect the immune system by blocking TNF have been associated with an increased risk of reactivation of latent tuberculosis (TB). It is possible that taking drugs such as anakinra that blocks IL-1 increases the risk of TB or other atypical or opportunistic infections. (Section 5.1 of the USPI)

Hypersensitivity reactions – Hypersensitivity reactions, including anaphylactic reactions and angioedema have been reported with anakinra. If a severe hypersensitivity reaction occurs, administration of anakinra should be discontinued and appropriate therapy initiated. (Section 5.3 of the USPI)

Immunosuppression – The impact of treatment with anakinra on active and / or chronic infections and the development of malignancies is not known. (Section 5.4 of the USPI)

15.37 Known potential toxicities:

>10% of patients:

Local: Injection site reaction (majority mild, typically lasting 14-28 days, characterized by erythema, ecchymosis, inflammation, and pain). Infection (Upper respiratory infections were 14% in the combined studies while serious infections were only 2%).

1% to 10% of patients: Hematologic: neutropenia

Miscellaneous: Headache, Immunogenicity to Anakinra.

<1% of patients (limited to important or life-threatening):

Hypersensitivity reactions (including anaphylaxis, angioedema, pruritus, rash, urticarial)

15.38 Drug procurement: As of October 31, 2018. Available from commercial supply. Note: Previously provided by SOBI, AB.

15.39 Nursing Guidelines:

- 15.391 Instruct patients on self-administration of anakinra and monitoring of injection sites. Be sure to instruct patient on rotating injection sites - injection sites should be at least 1 inch away from previous injections.
- 15.392 Allow solution to warm to room temperature over 60-90 minutes. Do not shake.
- 15.393 Patients should not receive live vaccines while on agent.
- 15.394 Instruct patient about injection site reactions which can last anywhere from 14-28 days. Instruct patient to contact PI if they have concerns about injection site reactions.
- 15.395 Warn patients of infection risk. Instruct patients to report any fever, or other signs/symptoms of infection to the study team.
- 15.396 Patients may experience headache. Treat symptomatically and monitor for effectiveness.
- 15.397 Although less common, gastrointestinal side effects (diarrhea and nausea), may be seen. Treat symptomatically and monitor for effectiveness.

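### Section 8.11 and the Table 8.2 thromboembolic row give incompatible lenalidomide doses for the next cycle, and no passage says which governs

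*Combined protocol and SAP*

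**What the plan says.** **The new-cycle rule (8.11).** The bolded sentence has two triggers: "If lenalidomide dosing was omitted for the remainder of the previous cycle or if the new cycle is delayed due to toxicity newly encountered" at the planned Day 1. In either case, "then the new cycle will be started with a one-level dose reduction of lenalidomide". No event or causative drug is excepted.

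**Table 8.2, thromboembolic event of Grade 3 or higher, Day 15 or later.** "Omit lenalidomide for remainder of cycle and start anticoagulation. Maintain dose level in next cycle".

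**Table 8.2, febrile neutropenia, Day 15 or later.** The cell orders omission for the rest of the cycle, refers to 8.11 and reduces one level. It then adds that, if neutropenia is the only reason for a reduction, "G-CSF may be used and the lenalidomide dose maintained for the next cycle at the investigator's discretion".

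**Start conditions (8.11).** One condition for opening a cycle on time is: "Any drug-related injection site reaction or peripheral sensory neuropathy that may have occurred has resolved to" Grade 1 or lower. If it is not met, the cycle waits.

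**Attribution sentence heading 8.2 and 8.3.** "Dose reductions of one drug and not the other may be done at the investigators discretion based on attribution of adverse events", with neutropenia as the exception (lenalidomide first).

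**How binding the rules are.** Section 8.0 makes the modifications strict for two cycles and guidelines afterwards. A note after the 8.4 table lets a dose lowered at the start of a cycle go back up one level at a time, at the investigator's discretion, once a cycle passes without further events above Grade 2.

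**The concern.** A dosing rule has to give one answer for one patient and one event. Here a patient whose lenalidomide is stopped late in a cycle for a thromboembolic event is told in one place to restart lower and in another to restart at the same level. Two investigators who each follow the protocol faithfully could give different doses of the backbone drug, and either dose could be recorded as a deviation.

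The injection site condition raises a related problem. Lenalidomide is swallowed (15.14) and the only injected agent is anakinra or placebo (7.12), yet the drug that 8.11 reduces is lenalidomide. Because 15.37 lists injection site reaction as an anakinra effect and the placebo in 15.32 is saline, it is natural to ask whether the rule could lower lenalidomide exposure more in one arm than in the other.

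**Working it through.** The main point needs a comparison of texts. Only the dose difference needs arithmetic. The plan states no figure on this point to reproduce.

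**Step 1. Test 8.11 against the Day 15 or later column of Table 8.2.** Every row below orders omission for the remainder of the cycle, so every row meets the first trigger in 8.11.

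| Table 8.2 row | Next-cycle dose in the table | Next-cycle dose in 8.11 | Consistent? |
|---|---|---|---|
| Platelets, rash Grade 2-3, sensory neuropathy Grade 3, thyroid, other non-hematologic | One level lower | One level lower | Yes |
| Allergic reaction Grade 2-3 | One level lower once resolved to Grade 1 or less | One level lower | Yes |
| Febrile neutropenia, G-CSF option not used | One level lower | One level lower | Yes |
| Febrile neutropenia, G-CSF option used | May be maintained | One level lower | Not as 8.11 is written |
| Thromboembolic event Grade 3 or higher | Maintained | One level lower | **No** |

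The Grade 4 rash, neuropathy and allergic rows stop lenalidomide, so no next-cycle dose arises. The Days 2-14 thromboembolic cell leaves the restart to the investigator and does not itself order omission for the rest of the cycle, so it is not counted as a conflict. One row contradicts 8.11 outright, and one contains an option that 8.11 does not carry.

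**Step 2. Size of one level (8.1).**

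- Daily dose at the first step: 25 mg to 15 mg; (25 − 15) / 25 = 40%.
- Per cycle over 21 days: 25 × 21 = 525 mg against 15 × 21 = 315 mg, a difference of 210 mg.
- Later steps: (15 − 10) / 15 = 33%; (10 − 5) / 10 = 50%.

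**Step 3. Follow an injection site reaction through the text.**

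- Grade 2, first met on Day 1: the start condition fails, the cycle is delayed, the second trigger in 8.11 is met, and lenalidomide drops one level. Section 8.3 has no anakinra/placebo action for it, because its general non-hematologic row begins at Grade 3. The written steps therefore change only lenalidomide.
- Grade 2, carried over from the previous cycle: the cycle may still be delayed, but the toxicity is not clearly new on Day 1, so the trigger is not clearly met. The protocol does not define the term.
- The attribution sentence would allow lenalidomide to be spared. It is permissive, whereas 8.11 is mandatory, and no order of precedence is given.

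**Step 4. Can a between-arm difference be sized?** Section 15.37 puts the reaction among effects in more than 10% of patients and describes it as "Injection site reaction (majority mild, typically lasting 14-28 days". The documents give no rate at Grade 2 or higher, no rate first met on Day 1, and no rate on placebo. For scale only, suppose an extra share *p* of anakinra patients sat at 15 mg instead of 25 mg. The arm's mean daily dose would fall by *p* × 10 mg. For an assumed *p* of 2% to 20%, that is 0.2 to 2.0 mg, or 0.8% to 8% of 25 mg. Nothing in the documents places the true value within that range.

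**The case against.** **The specific row overrides the general rule.** This is the best defence. The thromboembolic row omits the pointer to 8.11 that most Day 15 or later rows carry, which could mark it as a deliberate exception. But the allergic reaction row omits the pointer too and agrees with 8.11. The headings also point the other way: 8.11 is about starting a new cycle, and 8.2 is about changes during one. Either reading is arguable, which is why the text needs a decision.

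**The G-CSF wording is ordinary drafting.** The row follows 8.11 first and then states a conditional, discretionary exception. That largely stands. It is a secondary point: 8.11 should acknowledge the option.

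**The rules are softer than they look.** Attribution discretion, guideline status after two cycles and possible re-escalation all stand. They limit how long a 40% reduction need last, and they mean 8.11 does not rigidly force a lenalidomide cut for an injection site reaction. They do not remove the thromboembolic contradiction, least of all in the first two cycles.

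**A stronger reading that should be resisted.** A reader might infer that the anakinra arm will lose lenalidomide dose, and that the time-to-progression comparison is therefore biased and confounded. The documents do not support this, for three reasons:

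- The rates needed are absent, most reactions are described as mild, and the control arm also receives injections.
- Reactions that begin in the first month and last 14-28 days would mostly be carried over, and these do not clearly meet the Day 1 trigger.
- Section 2.12 compares two regimens. A lenalidomide reduction caused by intolerance after randomization is part of the assigned regimen's effect and is not confounding.

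Nor does the listing of deep vein thrombosis and pulmonary embolism at 10% or more (15.17) show how often the main conflict would arise. That listing is neither graded nor timed, and the conflict needs Grade 3 or higher on Day 15 or later.

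**Conclusion.** The contradiction between 8.11 and the Day 15 or later thromboembolic row is real and follows from the text alone. For a patient at the starting dose it is a choice between 25 mg and 15 mg a day, a 40% difference, with no stated order of precedence and with strict adherence required in the first two cycles.

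Two secondary inconsistencies stand. The G-CSF option is missing from 8.11. A Grade 2 injection site reaction first met on Day 1 leads literally to a change in the oral drug alone, against the sense of the attribution sentence. A resulting difference in lenalidomide exposure between arms is possible, and if it occurred it would mean less lenalidomide in the anakinra arm, but its size cannot be calculated from the documents. No claim of bias in the primary comparison, and no count of affected patients, is justified.

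The conclusion assumes that no other current text sets the precedence. It takes no view on which dose is clinically right. It is worth correcting because it bears directly on patient dosing and is cheap to settle.

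**What to change.** Amend Section 8 so that each event leads to one next-cycle instruction:

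1. Reconcile 8.11 with the thromboembolic row, either by naming the exception in 8.11 or by changing the row.
2. Make 8.11 and the G-CSF option in the febrile neutropenia row refer to each other consistently.
3. State which drug's dose, if any, changes after a Day 1 delay for an injection site reaction, consistently with the attribution sentence and 8.3, and define what counts as newly encountered.
4. Add a sentence saying which text governs if 8.11 and a table row differ.

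The clinical content of each choice belongs to the sponsor. The cost is one short wording amendment, with no effect on sample size or analysis. Optionally, tabulate lenalidomide exposure by arm beside the time-to-progression result, from dosing data already collected. That would show whether the arms differed in practice.
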